## PFIZER CONFIDENTIAL

CT24-WI-GL02-RF02 1.0 Non-Interventional Study Protocol Template For Secondary Data Collection Study 15-Aug-2018 Page 27 of 42 that pose no significant health problem in the neonatal period and tend to have limited social or cosmetic consequences for the affected individual. Examples include single palmar crease and clinodactyly.

## **Spontaneous Reports of Pregnancy Exposure**

Data contained in spontaneous sources and other data sources may be collected from patients, health care providers, lawyers, health authorities, other companies, the medical literature, and other sources, within the conduct of a NI Other Primary Data Collection Study spontaneous report or a report from other data sources. Data can be collected for a spontaneous report using the NIS Serious Adverse Event Report Form. This form is to be faxed to the local DSU and this data will be entered by the DSU into ARGUS and follow up will be performed per standard follow–up practices.

## 8.7. Data Analysis

Given the expected low number of reported pregnancy exposures, no formal data analysis or hypothesis testing will be conducted. Data collected on exposures and outcomes will be summarized descriptively. Summaries of the numbers of pregnancies and incidence proportion (percent) of adverse pregnancy and birth events reported via TESPO and/or captured in the standard EDP or SAE form entered into ARGUS will be provided. Women with ATTR exposed during pregnancy to concomitant medications with a known increased risk for congenital anomalies will be excluded from the descriptive summary but will be included in the study and described separately.

There are no known epidemiologic data on the incidence of adverse pregnancy outcomes in the ATTR population. Therefore, epidemiologic data on the incidence of adverse pregnancy outcomes in other populations (eg, the general population, particularly in those regions where tafamidis is commercially available and tafamidis unexposed pregnancies reported in THAOS) may be used to contextualize the findings.

A separate descriptive summary based on prospective and retrospective cases will be performed and submitted to the Agency. Prospective cases are defined as women who enroll prior to the occurrence of the pregnancy outcome (live birth, miscarriage, stillbirth, pregnancy termination). Retrospective cases are defined as women who enroll or contact the registry after the pregnancy outcome has occurred (live birth, miscarriage, stillbirth, pregnancy termination). Stratified analysis of the reported pregnancy outcomes, including pregnancies in women reported prior to start of this protocol, will be performed by daily maternal dose.

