## 6. RATIONALE AND BACKGROUND

VYNDAQEL® (tafamidis meglumine 20 mg capsule) once daily was first approved in the EU for transthyretin amyloid polyneuropathy (ATTR-PN), also known as transthyretin familial amyloid polyneuropathy (TTR-FAP) under exceptional circumstances on 16 November 2011. The product has been approved for ATTR-PN in over 40 other countries since then. TESPO, a worldwide approach to enhanced surveillance of pregnancy and birth outcomes in women with ATTR-PN exposed to tafamidis, was implemented as an additional pharmacovigilance activity in the EU Risk Minimization Plan (RMP), classified as a category 3 post-authorization measure (PAM), and has been in effect since 2011. As of 25 September 2019, there were 20 cases of exposure in utero to tafamidis, of which 13 were maternal exposure, during or within 1 month prior to pregnancy in the overall tafamidis program (clinical and non-interventional studies: Fx-005 (1); Fx1A-303 (2); Transthyretin Amyloidosis Outcomes Survey [THAOS](17).

On 03 May 2019, with the US approval of VYNDAQEL® once daily at a dose of 80 mg (tafamidis meglumine 4 x 20 mg capsules), and VYNDAMAX® (tafamidis 61 mg capsule) once daily for transthyretin amyloid cardiomyopathy (ATTR-CM), FDA required a post-marketing requirement (PMR 3576-1). To meet this post-marketing requirement (PMR 3576-1), this study will describe birth outcome frequency within the reported pregnancies in women with ATTR exposed to tafamidis during or within 1 month prior to pregnancy that are collected using the ongoing TESPO surveillance program and/or standard EDP and follow-up information collected in interventional studies.

In addition to US approval, tafamidis for the treatment of patients with ATTR-CM has been approved in Japan, United Arab Emirates, Brazil Canada, European Union, Singapore, Switzerland and Australia at this time.

This descriptive non-interventional study is designated as a Post-Authorization Safety Study (PASS) and is a commitment to the US FDA.

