## 6.2.2. Relevant Nonclinical Findings

There was no evidence of adverse effects of tafamidis on fertility, or reproductive performance, or mating behavior in rats. In animal reproductive studies, oral administration of tafamidis meglumine to pregnant rabbits during organogenesis resulted in adverse effects on development (embryofetal mortality, fetal body weight reduction and fetal malformation) at a dose providing approximately 9 times the human exposure area under the curve (AUC) at the maximum recommended human dose (MRHD), and increased incidence of fetal skeletal variations at a dose providing equivalent human exposure (AUC) at the MRHD. Postnatal mortality, delayed male sexual maturation, and impaired learning and memory were observed in offspring of pregnant rats administered tafamidis meglumine during gestation and lactation at a dose approximately 2 times the MRHD based on body surface area (mg/m^2).

Nonclinical studies with tafamidis indicate that there are no effects on the male germ cell before conception. In toxicology studies there was no evidence of genotoxicity, no histopathological changes in testis or epididymis and no effects on male fertility at doses up to 30 mg/kg. Therefore, the risk for male-mediated developmental toxicity is considered to be low because the levels of tafamidis estimated to be transferred in semen are significantly lower than the concentrations that cause developmental toxicity in nonclinical studies.

In summary, anomalies have been observed in rabbit and rat reproductive toxicology studies. In humans, ATTR could present during the patient's reproductive years, although based on our current understanding of age of onset of disease, this is more likely for a patient with ATTR-PN rather than ATTR-CM. On account of the low prevalence of ATTR-PN and ATTR-CM (rare diseases), limited reproductive data are available in humans. There has been a low incidence of exposures reported in women with ATTR-PN in the ongoing TESPO surveillance program from clinical and NI studies over a 7-year period. Nonetheless, given that tafamidis meglumine/tafamidis may cause fetal harm, product labeling recommends avoidance of pregnancy in female patients receiving tafamidis; breastfeeding is also not recommended during treatment with tafamidis. B3461091 will collect and summarize data on pregnancy outcome and birth outcome in women with ATTR exposed to tafamidis during or within 1 month prior to pregnancy.

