## 8.5. Study Size

Sample size calculations are not applicable. All pregnant women diagnosed with ATTR meeting the inclusion criteria presented in Section 8.2.1 will be included in this study.

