#### PFIZER CONFIDENTIAL

CT24-WI-GL02-RF02 1.0 Non-Interventional Study Protocol Template For Secondary Data Collection Study 15-Aug-2018 Page 39 of 42

Section 9: Data sources	Yes	No	N/A	Section Number
9.2.1 Exposure? (eg, date of dispensing, drug quantity, dose, number of days of supply prescription, daily dosage, prescriber).				
9.2.2 Outcomes? (eg, date of occurrence, multiple event, severity measures related to event).	$\boxtimes$			8.3
9.2.3 Covariates and other characteristics? (eg, age, sex, clinical and drug use history, co-morbidity, co-medications, lifestyle).	$\boxtimes$			8.3
9.3 Is a coding system described for:				
9.3.1 Exposure? (eg, WHO Drug Dictionary, Anatomical Therapeutic Chemical (ATC) Classification System).		$\boxtimes$		
9.3.2 Outcomes? (eg, International Classification of Diseases (ICD), Medical Dictionary for Regulatory Activities (MedDRA)).	$\boxtimes$			10
9.3.3 Covariates and other characteristics?			$\square$	
9.4 Is a linkage method between data sources described? (eg, based on a unique identifier or other).	$\boxtimes$			9

Sectio	Section 10: Analysis plan		No	N/A	Section Number
10.1	Are the statistical methods and the reason for their choice described?				8.7
10.2	Is study size and/or statistical precision estimated?			$\boxtimes$	
10.3	Are descriptive analyses included?	$\boxtimes$			8.7
10.4	Are stratified analyses included?			$\boxtimes$	
10.5	Does the plan describe methods for analytic control of confounding?				
10.6	Does the plan describe methods for analytic control of outcome misclassification?				
10.7	Does the plan describe methods for handling missing data?				
10.8	Are relevant sensitivity analyses described?		$\square$		
Comme	nts:				

Sectio	n 11: Data management and quality control	Yes	No	N/A	Section Number
11.1	Does the protocol provide information on data storage? (eg, software and IT environment, database maintenance and anti-fraud protection, archiving).				8.6.1
11.2	Are methods of quality assurance described?	$\square$			8.8
11.3	Is there a system in place for independent review of study results?				11

Sectio	Section 12: Limitations		No	N/A	Section Number
12.1	Does the protocol discuss the impact on the study results of: 12.1.1 Selection bias? 12.1.2 Information bias? 12.1.3 Residual/unmeasured confounding? (eg, anticipated direction and magnitude of such biases, validation sub-study, use of validation and				8.9

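### Section 8.7 plans incidence percentages from very few pregnancies with no measure of uncertainty; small numbers justify dropping hypothesis tests, but not the interval

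*Protocol*

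**What the plan says.** Section 8.7 of the protocol gives the low expected number of exposures as its reason that "no formal data analysis or hypothesis testing will be conducted". The abstract takes the same decision for the same reason. Section 8.7 then names the output: "Summaries of the numbers of pregnancies and incidence proportion (percent) of adverse pregnancy and birth events". It mentions no confidence interval or other measure of precision.

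The same section allows epidemiologic data from other populations to be used as context. The examples it gives are the general population and unexposed pregnancies in THAOS. It also divides the data: prospective and retrospective cases are summarized separately, women exposed to co-medication with a known malformation risk leave the main summary, and outcomes are stratified by daily maternal dose. The dose analysis also brings in pregnancies reported before the study began.

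Section 8.5 says "Sample size calculations are not applicable". In Annex 1, checklist item 10.2 ("Is study size and/or statistical precision estimated") is marked not applicable, as far as the extracted text shows. Section 8.9 lists the small number of pregnancies as its first limitation and says it may limit interpretability, without a figure. The only accrual history is in Section 6: "As of 25 September 2019, there were 20 cases of exposure in utero to tafamidis, of which 13 were maternal exposure".

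**The concern.** A small expected number is a good reason not to test hypotheses. It is no reason to leave a percentage without an interval, since the fewer the pregnancies, the less a percentage says by itself. Section 8.7 draws both consequences from the same premise.

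The study is meant to assess risks to the pregnancy, fetus and neonate under an FDA post-marketing requirement, with ten annual interim reports and a final report. Once a percentage stands beside a background rate, the reader is making a comparison, even if an informal one. Without an interval the reader cannot tell whether a reported 0% excludes a risk of 5% or only one above 20%, nor whether a single event is a signal or chance. The early interim reports will have the smallest denominators.

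**Working it through.** The protocol states no sample size, power or precision, so there is no planned figure to reproduce. Its one countable figure agrees with itself: the cases by source in Section 6 are 1 + 2 + 17 = 20.

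**Inputs**
- 13 maternal exposures up to 25 September 2019 (Section 6).
- Assumed start of accrual: first EU approval, "under exceptional circumstances on 16 November 2011" (Section 6). To 25 September 2019 this is 7.86 years.
- Alternative accrual period: 7 years, from Section 6.2.2 ("in the ongoing TESPO surveillance program from clinical and NI studies over a 7-year period").
- Collection period: 28 April 2020 (protocol date) to 30 June 2030, 10.17 years. Section 5 gives the months only.
- Confidence level: 95%, two-sided, exact. This is an assumption; the protocol gives none.

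**Expected number, assuming a constant rate**
- 13 / 7.86 = 1.65 per year; 1.65 × 10.17 = 16.8, about 17.
- With 7 years: 13 / 7 × 10.17 = 18.9, about 19.
- Exact Poisson 95% limits on a count of 13 are 6.9 and 22.2. Multiplied by 10.17 / 7.86, they give about 9 to 29. This range reflects only the uncertainty in the past rate; the number actually reported would vary further.

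**Exact (Clopper-Pearson) 95% intervals**

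For zero events the upper limit is 1 − 0.025^(1/N). For x events the limits are the 2.5% quantile of Beta(x, N − x + 1) and the 97.5% quantile of Beta(x + 1, N − x).

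| Events / N | Percent | 95% interval |
|---|---|---|
| 0/8 | 0 | 0 to 36.9% |
| 0/17 | 0 | 0 to 19.5% |
| 1/17 | 5.9 | 0.1 to 28.7% |
| 2/17 | 11.8 | 1.5 to 36.4% |
| 0/19 | 0 | 0 to 17.6% |
| 0/30 | 0 | 0 to 11.6% |

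The row for 30 is close to the top of the accrual range. It also matches 17 new plus 13 earlier pregnancies, the pool for the dose-stratified analysis before it is split. The row for 8 stands for a subset or an early interim report.

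**Chance of seeing nothing.** With N = 17 and true risk p, the probability of zero events is (1 − p)^17. For assumed risks of 3%, 6%, 9% and 15% it is 60%, 35%, 20% and 6%. At an assumed risk of 10%, zero or one event occurs 48% of the time.

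**Denominators by outcome.** Birth weight, Apgar score and infant milestones are measured only in live-born infants, so their N is below the number of pregnancies. The co-medication exclusion and the prospective/retrospective split reduce it further.

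**The case against.** The strongest objection is that whether a descriptive table carries an interval is commonly settled in a statistical analysis plan, and one may exist. Section 8.7 rules out formal analysis and testing, but an interval around a proportion can count as descriptive and nothing expressly forbids it. It is right that the text does not prohibit intervals, and a reader who infers a prohibition goes too far. But Section 8.7 is not merely silent. It gives a reason for having no formal analysis, names percentages as the output and opens the way to external context, and the protocol text at hand refers to no separate plan. The wording points away from intervals.

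A reader might also infer that a zero or single-event result is bound to look far more reassuring than it should. The documents do not support that. One event in 17 shows as 5.9%, which could alarm rather than reassure beside a low background rate. False reassurance is a risk mainly with zero events. Section 8.9 also warns about small numbers, counts are to be reported as well as percentages, and the external comparison is optional.

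The figure of 17 is open to challenge as well. It is an extrapolation, unrelated to the 17 THAOS cases in Section 6, which are a share of all 20 exposures and not of the 13 maternal ones. The 13 come from the whole program, including clinical studies, so approval may not mark the start of accrual. The rate may also change with the cardiomyopathy indication and the planned awareness efforts, although Section 6.1 expects few pregnancies in cardiomyopathy patients.

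Finally, reporting is voluntary and incomplete (Section 8.9), so a binomial interval could suggest more rigor than the data have. That stands, and calls for a caveat beside the interval.

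**Conclusion.** The point holds as one of imprecision in both directions. Section 8.7 and the abstract use small numbers to justify having no formal analysis and plan percentages with no measure of uncertainty, though these may be read against external rates. Omitting hypothesis tests is right for a descriptive surveillance study, and treating sample size as not applicable is ordinary when every reported case is included.

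The exact size depends on the assumed accrual and the 95% level, but the conclusion does not. Even with 30 pregnancies, zero events would leave a risk of 11.6% within the interval. A single precision figure based on all pregnancies would be too optimistic for outcomes with smaller denominators. The acknowledgment in Section 8.9 is fair but gives the reader no scale.

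**What to change.** In Section 8.7 and the data analysis paragraph of the abstract, replace the sentence that rules out formal analysis with:

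> *No hypothesis tests will be conducted. Each incidence proportion will be reported as n/N, with the denominator relevant to that outcome, and an exact (Clopper-Pearson) two-sided 95% confidence interval, including when n = 0. The intervals reflect sampling error only and do not account for selective or incomplete reporting.*

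In Section 8.9, add the zero-event upper limit over a range of denominators, for example 36.9% at 8, 19.5% at 17 and 11.6% at 30. State that these denominators are assumptions and not forecasts.

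The cost is a short text change in three places and one more column in the summary tables. No additional data are needed. The small downside is that the intervals will be wide and must be read with the reporting-bias caveat.

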## 8.2.2. Exclusion Criteria

There are no exclusion criteria for this study.

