Other relevant medical conditions, use of concomitant medications, other exposures to drugs	Comorbities/hospitalizations during pregnancy/other concomitant medications or treatments taken during pregnancy	EDP form		
Maternal assessment at delivery				
Smoking during pregnancy	Type and number per day	EDP form		
Alcohol use during pregnancy Type and frequency		EDP form		
Other relevant medical conditions, use of concomitant medications, other exposures to drugs	onditions, use of oncomitantduring pregnancy/other concomitant medications or treatments taken during			
Child status				
Neonate health status at birth	Gender, head circumference, length (cm or in), birth weight (kg or lbs)	EDP form		
	Survival, any congenital anomalies diagnosed,			

Variable	Description	Data Source
	(chromosomal testing results if performed), any medical conditions diagnosed/treated	
Neonate developmental status	Age-appropriate developmental milestones achieved or delayed	EDP form
Infant exposure during breast-feeding	Length of exposure, any interruptions in exposure	Tafamidis enhanced surveillance follow up form
Infant health status at 6 months	Survival, any congenital anomalies diagnosed, (chromosomal testing results if performed), any medical conditions diagnosed/treated	Revised form
	Weight (kg or lbs), length (cm or in), Hospitalizations during the	
	first 6 months	
Infant developmental status at 6 months	Age-appropriate developmental milestones achieved or delayed	Revised form
Child status at 12 months		
Health status at 12 months	Survival, any congenital anomalies diagnosed, (chromosomal testing results if performed), any	Tafamidis enhanced surveillance

Variable	Description	Data Source
	medical conditions diagnosed/treated Weight (kg or lbs), length (cm or in), Hospitalizations during the first year	follow up form
Developmental status of infant at 12 months	Age-appropriate developmental milestones achieved or delayed	Tafamidis enhanced surveillance follow up form
Medication/vaccination status at 12 months	Medications taken during the first year, vaccinations received	Tafamidis enhanced surveillance follow up form

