## Serious Adverse Event Exposure During Pregnancy Supplemental Report (EDP) Form

This form is to be completed for all reported exposures during pregnancy, regardless of source of report. Upon receipt of information concerning an exposure to tafamidis of a woman during or within 1 month prior to pregnancy, or a reported pregnancy occurring within one month of tafamidis discontinuation, the reporter will complete a standard EDP form. This form is to be submitted to the local Pfizer DSU. If the initial contact is not an obstetric HCP, women will be requested to sign and send a release form to the reporter, which authorizes the Sponsor to contact the obstetric HCP for additional information. When the EDP report is received by the local Pfizer DSU, the local Pfizer DSU staff enters the information contained in the EDP Form into Pfizer's global safety database (ARGUS) and follows up with the investigator per standard follow–up practices for missing/discrepant/clarifying information. The investigator addresses DSU queries for clarifying the initial EDP report and will complete the query form or an additional EDP form.

The initial completed form will collect basic demographic information, medical and obstetrical history (for patient and family), pregnancy information including estimated due date and dates of all drug exposures within 1 month of pregnancy.

At the midpoint of the pregnancy and the estimated time of delivery, the obstetric HCP will be asked to complete an additional standard EDP form with reference to the status and outcome of the pregnancy. The local Pfizer DSU staff enters the information contained in the EDP Form into Pfizer's global safety database (ie, Argus) and follows up with the HCP per standard follow–up practices for missing/discrepant/clarifying information. The HCP addresses DSU queries for clarifying the follow up EDP report and will complete the query form or an additional EDP form. This form will be submitted to the local Pfizer DSU by fax (or email, if approved by Pfizer).

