## Tafamidis Enhanced Surveillance for Pregnancy Outcomes (TESPO) 6 and 12-Month Infant Follow-up

In the event of a live birth, the obstetric HCP will be sent a release form to be signed by the female individual to allow the Sponsor to contact the infant's pediatric HCP for additional infant outcome data. The Sponsor will contact the pediatric HCP to complete the TESPO Infant 6 and 12-Month Follow-up Form by phone or fax.

If anomalies are noted on the EDP Form or the TESPO Infant Follow-up Forms, a more detailed investigation may be initiated by the Sponsor.

Measures of pregnancy and birth outcomes	Common abbreviation	Definition
Preterm birth	РТВ	Birth at less than 37 completed weeks of gestation
Very preterm birth	VPTB	Birth at less than 32 completed weeks of gestation
Low birth weight	LBW	Weighing less than 2,500 grams (~5.5 pounds) at delivery
Very low birth weight	VLBW	Weighing less than 1,500 grams (~3.3 pounds) at delivery
Infant mortality	IM	Death of a live-born infant before the first birthday
Fetal death (stillbirth)	FD	Death of a fetus after the 20 th week of gestation
Spontaneous fetal losses	SFL	Recognized pregnancies that do not result in induced abortions or live births; includes miscarriages, ectopic (tubal) pregnancies, and FD

Centers for Disease Control (CDC) - Measures of birth and pregnancy outcomes

Definition of SFL from Ventura SJ, et al. 2004.

According to the CDC congenital anomalies comprise a wide range of abnormalities of body structure or function that are present at birth and are of prenatal origin. For efficiency and practicality, the focus is commonly on *major* structural anomalies. These are defined as structural changes that have significant medical, social or cosmetic consequences for the affected individual, and typically require medical intervention. Examples include cleft lip and spina bifida. Major structural anomalies are the conditions that account for most of the deaths, morbidity and disability related to congenital anomalies. In contrast, minor congenital anomalies, although more prevalent among the population, are structural changes

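### Section 8.7 removes women on malformation-risk co-medication from the summary without fixing that status before the outcome, so exclusion can depend on the outcome, and no all-eligible percentage is promised

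*Protocol*

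**What the plan says.** Section 8.7 plans no hypothesis testing. The result is a descriptive summary giving the "incidence proportion (percent) of adverse pregnancy and birth events reported via TESPO" or entered through the standard forms. From that summary, "Women with ATTR exposed during pregnancy to concomitant medications with a known increased risk for congenital anomalies will be excluded from the descriptive summary". The same sentence keeps these women in the study, with a description of their own. The Abstract repeats the rule. Neither place names a drug list, a data cut-off relative to the outcome, or classification blind to outcome, and neither limits the rule to malformations.

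Co-medication reaches the sponsor at several times:

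- **First report.** The initial exposure-during-pregnancy (EDP) form, required for every reported exposure, collects "pregnancy information including estimated due date and dates of all drug exposures within 1 month of pregnancy". Section 8.3 also lists malformation-risk co-medication, with dose and dates, as an EDP variable.
- **Mid-pregnancy and delivery.** At both times "the obstetric HCP will be asked to complete an additional standard EDP form with reference to the status and outcome of the pregnancy". In Section 8.3 the block headed "Maternal assessment at delivery" again lists concomitant medication.
- **After an anomaly.** "If anomalies are noted on the EDP Form or the TESPO Infant Follow-up Forms, a more detailed investigation may be initiated by the Sponsor". Under Section 8.6.1, infant adverse events also open a separate linked case with its own follow-up.
- **Retrospective cases.** These are accepted, and by definition they are first reported after the outcome.

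Section 8.7 plans separate prospective and retrospective summaries and a stratification by daily dose. It does not say whether the exclusion applies within them. For context it names other populations, such as the general population, and unexposed pregnancies in the THAOS survey.

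**The concern.** Restricting on an exposure is harmless to a percentage when the exposure is classified in the same way whatever the outcome. Here the classification stays open until after the outcome is known. A malformed child gives more occasions on which a co-medication might come to light, and a mother who is then classed as co-exposed leaves the numerator. If an equivalent co-medication is missed more often when the child is normal, that pregnancy stays in the denominator. Section 8.9 does not list this among the limitations.

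The stake is the main safety figure for a drug with fetal malformations in rabbits (Section 6.2.2), where an error towards reassurance is the costly one. A second problem does not depend on timing. The summary excludes a group at higher risk, while the figures meant to put it in context are not described as excluding the same group.

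**Working it through.** **1. Inputs.** The Protocol gives no sample size, target rate or precision, so it has no figure to reproduce. Section 6 reports 20 in-utero exposures (1 + 2 + 17 = 20 by study, which agrees), of which 13 were maternal. If counting began at EU approval on 16 November 2011, which the Protocol does not say, 13 / 7.86 years = 1.65 per year. Over April 2020 to June 2030 that is 1.65 × 10.25, or about 17 pregnancies.

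**2. Effect of moving one case** (exact 95% intervals):

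- 13 pregnancies: 1/13 = 7.7% (0.2 to 36.0) becomes 0/12 = 0% (0 to 26.5).
- 17 pregnancies: 1/17 = 5.9% becomes 0/16 = 0%.

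The intervals overlap heavily. The step shows how few cases there are; it does not measure bias.

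**3. Direction of the effect.** Let q be the share using such a co-medication, pu and pe the malformation risk without and with it, and s1 and s0 the share of true use that is found in malformed and in other pregnancies. If nobody is wrongly excluded,

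observed risk = [(1−q)·pu + q·pe·(1−s1)] / {[(1−q)·pu + q·pe·(1−s1)] + [(1−q)(1−pu) + q(1−pe)(1−s0)]}.

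This falls below pu only if (1−s1)/(1−s0) < 1/OR, where OR is the co-medication's own odds ratio for malformation.

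All values below are assumptions, since the Protocol gives none. Take pu = 3% and q = 20%. Example with OR 3, s1 = 0.9, s0 = 0.6: pe = 8.49%; malformed retained = 0.024 + 0.0017 = 0.0257; others retained = 0.776 + 0.0732 = 0.8492; observed risk = 0.0257/0.8749 = 2.94%.

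| OR | s1 = s0 = 0.8 | s1 = 0.9, s0 = 0.6 | s1 = 1.0, s0 = 0.6 | All eligible |
|---|---|---|---|---|
| 1 | 3.00% | 2.80% | 2.73% | 3.0% |
| 3 | 3.26% | 2.94% | 2.75% | 4.1% |
| 5 | 3.49% | 3.06% | 2.76% | 5.1% |

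The last column is (1−q)·pu + q·pe; for OR 3 it is 0.8 × 3% + 0.2 × 8.49% = 4.1%.

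Over q = 10% to 30%:

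- Equal detection (0.8), OR 2 to 5: 3.06% to 3.82%, above the 3% target.
- s1 = 0.9, s0 = 0.6: 2.68% to 2.97% for OR 1 to 3, but 3.03% to 3.10% for OR 5.
- s1 = 1.0, s0 = 0.5 or 0.6: 2.48% to 2.89%.
- s1 = 0.9, s0 = 0.6, with 20% of unexposed malformed cases also wrongly excluded: 2.18% to 2.59%.

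**4. Comparison with background.** Against the all-eligible figure, exclusion lowers the percentage whenever the co-medication raises risk and is found at least as often in malformed cases. With OR 3 and equal detection, 4.1% becomes 3.3% without any outcome-dependent detection. That reduction is what restriction is meant to do, but setting 3.3% beside an unrestricted background rate would flatter the drug.

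**The case against.** A reader might infer that malformed cases are preferentially excluded and that the percentage is biased low as a matter of fact. The documents do not support that.

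- Exposure data are not gathered only after a bad outcome. Every case is asked on the initial form, which precedes the outcome in prospective cases, and the later forms are requested whatever the outcome.
- The further investigation after an anomaly is optional and is not said to cover maternal co-medication. The linked infant case applies to any infant adverse event and follows the standard safety process. That either leads to a fuller drug history is inference.
- The direction is conditional. With equal detection and a co-medication that truly raises risk, the restricted figure lies above the co-medication-free risk. Removing a malformed case truly exposed to such a drug is the purpose of the rule.

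A reader might also see a contradiction with Section 8.2.2, where "There are no exclusion criteria for this study". There is none, because the women remain in the study and only their place in the summary changes.

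Two further points carry weight. Excluded women are described separately, so an all-cases percentage might be rebuilt. Drug lists and sensitivity tables are also commonly left to a statistical analysis plan, which is not at hand.

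These points remove the claim of certain bias but not the concern. The exclusion is itself fixed in the Protocol, for all outcomes and without a cut-off. The Protocol does not undertake to show an all-eligible percentage, and splitting prospective from retrospective cases does not undo an exclusion made within either group.

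**Conclusion.** The concern holds as a permitted risk and a missing commitment. Section 8.7 allows a pregnancy to leave the main summary on information obtained after its outcome, and offers only the restricted percentage for comparison with backgrounds not described as restricted. Under the assumed values above, outcome-dependent detection moves a 3% risk to between about 2.2% and 3.1%, so a low result is plausible but not assured. These shifts are small beside the sampling error at 13 to 17 pregnancies. The practical issue is that reclassifying a single case can decide whether the headline is zero. The count of 17 rests on the assumed start of counting, and all detection rates, use rates and odds ratios are assumptions.

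**What to change.** In Section 8.7 and the Abstract:

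- Report each incidence proportion side by side, for all eligible pregnancies and with the co-exposed women excluded. Use the all-eligible figure when comparing with unrestricted background rates.
- For prospective cases, set exclusion status from co-medication recorded before the outcome (enrolment and second-trimester EDP forms), against a drug list fixed before the first interim report in April 2021. Describe co-medication found later in the narrative, without moving the case.
- For retrospective cases, classification before the outcome is impossible. Classify them against the same list blind to outcome, and show them only in their separate summary, with and without the exclusion. Blinding guards the judgement but cannot repair a drug history that was itself collected after the outcome; the report should say so.

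The cost is one extra table, a short paragraph and a drug list agreed early. The all-eligible percentage will include a few pregnancies with another possible cause, which the restricted column and the narratives make visible. Co-medication found late will stay in the restricted column for prospective cases; that is the price of keeping the outcome out of the classification.
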